3.2 CLINICAL LABORATORY EVALUATION

3.2.1 Available data

Per protocol, the following laboratory parameters are expected:

- Biochemistry: creatinine, glucose, aspartate aminotransferase (AST), alanine aminotransferase (ALT), alkaline phosphatase (ALP), gamma glutamylaminotransferase (GGT), C-reactive protein (CRP), bilirubin, sodium and potassium. Sodium and potassium tests are only required in the challenge period
- Haematology: haemoglobin, haematocrit, red blood cell (RBC) count, white blood cell (WBC) count with differential, platelet count, mean corpuscular haemoglobin (MCH), mean corpuscular haemoglobin concentration (MCHC), mean corpuscular volume (MCV)

Normal ranges are available as provided by the laboratory.

3.2.2 Derivation rules

Toxicity grades will be computed according to the Centre for Biologics Evaluation and Research (CBER) toxicity grading list. The implementation of these toxicity grades for analysis is presented in appendix 9.2. Only the parameters described in appendix 9.2 will be computed, according to the declared limits for each grade.

For parameters for which no toxicity grades are defined, the following abnormality categories will be defined:

- Low: value < lower limit of normal range
- Normal: lower limit of normal range \leq value \leq upper limit of normal range
- High: value > upper limit of normal range

Note:

- Classification will be done in standardised units, using non imputed values and limits.
- For the worst-case analysis visit, as defined in section 5.2.5, an additional category low + high is defined in case there are both low and high values within the same phase.

	Statistical Analysis Plan	
FLU010	Final analysis	Final 3.0 of 15JUN2020

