Potassium – Hypokalemia mEq/L	3.5 – 3.6	3.3 – 3.4	3.1 – 3.2	< 3.1
Glucose – Hypoglycemia mg/dL	65 – 69	55 – 64	45 – 54	< 45
Glucose – Hyperglycemia				
Fasting – mg/dL	100 – 110	111 – 125	>125	Insulin requirements or hyperosmolar coma
Random – mg/dL	110 – 125	126 – 200	>200	
Blood Urea Nitrogen BUN mg/dL	23 – 26	27 – 31	> 31	Requires dialysis
Creatinine – mg/dL	1.5 – 1.7	1.8 – 2.0	2.1 – 2.5	> 2.5 or requires dialysis
Calcium – hypocalcemia mg/dL	8.0 – 8.4	7.5 – 7.9	7.0 – 7.4	< 7.0
Calcium – hypercalcemia mg/dL	10.5 – 11.0	11.1 – 11.5	11.6 – 12.0	> 12.0
Magnesium – hypomagnesemia mg/dL	1.3 – 1.5	1.1 – 1.2	0.9 – 1.0	< 0.9
Phosphorous – hypophosphatemia mg/dL	2.3 – 2.5	2.0 – 2.2	1.6 – 1.9	< 1.6
CPK – mg/dL	1.25 – 1.5 x ULN***	1.6 – 3.0 x ULN	3.1 – 10 x ULN	> 10 x ULN
Albumin – Hypoalbuminemia g/dL	2.8 – 3.1	2.5 – 2.7	< 2.5	--
Total Protein – Hypoproteinemia g/dL	5.5 – 6.0	5.0 – 5.4	< 5.0	--
Alkaline phosphate – increase by factor	1.1 – 2.0 x ULN	2.1 – 3.0 x ULN	□ 3.1 – 10 x ULN	> 10 x ULN
Liver Function Tests –ALT, AST increase by factor	1.1 – 2.5 x ULN	2.6 – 5.0 x ULN	5.1 – 10 x ULN	> 10 x ULN
Bilirubin – when accompanied by any increase in Liver Function Test increase by factor	1.1 – 1.25 x ULN	1.26 – 1.5 x ULN	1.51 – 1.75 x ULN	> 1.75 x ULN
Bilirubin – when Liver Function Test is normal; increase by factor	1.1 – 1.5 x ULN	1.6 – 2.0 x ULN	2.0 – 3.0 x ULN	> 3.0 x ULN
Cholesterol	201 – 210	211 – 225	> 226	---
Pancreatic enzymes – amylase, lipase	1.1 – 1.5 x ULN	1.6 – 2.0 x ULN	2.1 – 5.0 x ULN	> 5.0 x ULN

* The laboratory values provided in the tables serve as guidelines and are dependent upon institutional normal parameters. Institutional normal reference ranges should be provided to demonstrate that they are appropriate.

** The clinical signs or symptoms associated with laboratory abnormalities might result in characterization of the laboratory abnormalities as Potentially Life Threatening (Grade 4). For example, a low sodium value that falls within a grade 3 parameter (125-129 mEq/L) should be recorded as a grade 4 hyponatremia event if the participant had a new seizure associated with the low sodium value.

*** ULN" is the upper limit of the normal range.

Hematology *	Mild (Grade 1)	Moderate (Grade 2)	Severe (Grade 3)	Potentially Life Threatening (Grade 4)
Hemoglobin (Female) - gm/dL	11.0 – 12.0	9.5 – 10.9	8.0 – 9.4	< 8.0
Hemoglobin (Female) change from baseline value - gm/dL	Any decrease – 1.5	1.6 – 2.0	2.1 – 5.0	> 5.0

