9.3 TOXICITY GRADES

Toxicity Grading Scale for Healthy Adult and Adolescent Volunteers Enrolled in Preventive Vaccine Clinical Trials, CBER, September 2007

PARAMETER	Unit	GRADE 1	GRADE 2	GRADE 3	GRADE 4
Amylase [pancreatic]		1.1-1.5 *ULN	>1.5-2.0 *ULN	>2.0-5.0 *ULN	>5.0 *ULN
Alanine amino transferase		1.1-2.5 *ULN	>2.5-5.0 *ULN	>5.0-10.0 *ULN	>10.0 *ULN
Albumin	g/L	31-28	<28-25	<25	-
	g/dL	3.1-2.8	<2.8-2.5	<2.5	-
Alkaline phosphatase		1.1-2.0 *ULN	>2.0-3.0 *ULN	>3.0-10.0 *ULN	>10.0 *ULN
Aspartate amino transferase		1.1-2.5 *ULN	>2.5-5.0 *ULN	>5.0-10.0 *ULN	>10.0 *ULN
Bilirubin [total]		1.1-1.5 *ULN	>1.5-2.0 *ULN	>2.0-3.0 *ULN	>3.0 *ULN
Blood urea nitrogen	mmol/L	8.2-9.3	>9.3-11.1	>11.1	-
	mg/dL	23-26	>26-31	>31	-
Calcium low	mmol/L	2.10-2.00	<2.00-1.87	<1.87-1.75	<1.75
	mg/dL	8.4-8.0	<8.0-7.5	<7.5-7.0	<7.0
Calcium high	mmol/L	2.62-2.74	>2.74-2.87	>2.87-2.99	>2.99
	mg/dL	10.5-11.0	>11.0-11.5	>11.5-12.0	>12.0
Cholesterol	mmol/L	5.20-5.43	>5.43-5.82	>5.82	-
	mg/dL	201-210	>210-225	>225	-
Creatinine	mmol/L	0.133-0.150	>0.150-0.177	>0.177-0.221	>0.221
	mg/dL	1.5-1.7	>1.7-2.0	>2.0-2.5	>2.5
Creatine [phospho] kinase		1.25-1.50 *ULN	>1.50-3.00 *ULN	>3.00-10.00 *ULN	>10.00 *ULN

	Statistical Analysis Plan				
	FLU010	Final analysis			Final 3.0 of 15JUN2020

Glucose fasting low	mmol/L	3.83-3.61	<3.61-3.05	<3.05-2.50	<2.50
	mg/dL	69-65	<65-55	<55-45	<45
Glucose fasting high	mmol/L	5.55-6.11	>6.11-6.94	>6.94	-
	mg/dL	100-110	>110-125	>125	-
Glucose non-fasting low	mmol/L	3.83-3.61	<3.61-3.05	<3.05-2.50	<2.50
	mg/dL	69-65	<65-55	<55-45	<45
Glucose non-fasting high	mmol/L	6.11-6.94	>6.94-11.10	>11.10	-
	mg/dL	110-125	>125-200	>200	-
Lipase		1.1-1.5 *ULN	>1.5-2.0 *ULN	>2.0-5.0 *ULN	>5.0 *ULN
Magnesium	mmol/L	0.62-0.53	<0.53-0.45	<0.45-0.37	<0.37
	mg/dL	1.5-1.3	<1.3-1.1	<1.1-0.9	<0.9
Phosphate	mmol/L	0.81-0.74	<0.74-0.65	<0.65-0.52	<0.52
	mg/dL	2.5-2.3	<2.3-2.0	<2.0-1.6	<1.6
Potassium low	mmol/L	3.6-3.5	<3.5-3.3	<3.3-3.1	<3.1
	mEq/L	3.6-3.5	<3.5-3.3	<3.3-3.1	<3.1
Potassium high	mmol/L	5.1-5.2	>5.2-5.4	>5.4-5.6	>5.6
	mEq/L	5.1-5.2	>5.2-5.4	>5.4-5.6	>5.6
Protein	g/L	60-55	<55-50	<50	-
	g/dL	6.0-5.5	<5.5-5.0	<5.0	-
Sodium low	mmol/L	134-132	<132-130	<130-125	<125
	mEq/L	134-132	<132-130	<130-125	<125

	Statistical Analysis Plan				
	FLU010	Final analysis			Final 3.0 of 15JUN2020

Sodium high	mmol/L	144-145	>145-147	>147-150	>150
	mEq/L	144-145	>145-147	>147-150	>150
Prothrombin time		1.00-1.10	>1.10-1.20	>1.20-1.25	>1.25

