Partial thromboplastin time		1.0-1.2	>1.2-1.4	>1.4-1.5	>1.5
Fibrinogen low	μmol/L	5.88-4.41	<4.41-3.68	<3.68-2.94	<2.94
	mg/dL	200-150	<150-125	<125-100	<100
Fibrinogen high	μmol/L	11.76-14.70	>14.70-17.65	>17.65	-
	mg/dL	400-500	>500-600	>600	-
Eosinophils	giga/L	0.65-1.50	>1.50-5.00	>5.00	-
	counts/mm ³	650-1500	>1500-5000	>5000	-
Hemoglobin [female] ^[1]	mmol/L	7.27-6.67	<6.67-5.76	<5.76-4.85	<4.85
	g/dL	12.0-11.0	<11.0-9.5	<9.5-8.0	<8.0
Hemoglobin [male] ^[1]	mmol/L	8.18-7.58	<7.58-6.36	<6.36-5.15	<5.15
	g/dL	13.5-12.5	<12.5-10.5	<10.5-8.5	<8.5
Hemoglobin, as decrease from baseline ^[2]	mmol/L	<0.00 to -0.91	<-0.91 to -1.21	<-1.21 to -3.03	<-3.03
	g/dL	<0.0 to -1.5	<-1.5 to -2.0	<-2.0 to -5.0	<-5.0
Lymphocytes [absolute count]	giga/L	1.00-0.75	<0.75-0.50	<0.50-0.25	<0.25
	counts/mm ³	1000-750	<750-500	<500-250	<250
Neutrophils [absolute count]	giga/L	2.0-1.5	<1.5-1.0	<1.0-0.5	<0.5
	counts/mm ³	2000-1500	<1500-1000	<1000-500	<500
Platelets	giga/L	140-125	<125-100	<100-25	<25

	Statistical Analysis Plan	
FLU010	Final analysis	Final 3.0 of 15JUN2020

	counts/mm ³	140000-125000	<125000-100000	<100000-25000	<25000
White blood cells low	giga/L	3.5-2.5	<2.5-1.5	<1.5-1.0	<1.0
	counts/mm ³	3500-2500	<2500-1500	<1500-1000	<1000
White blood cells high	giga/L	10.8-15.0	>15.0-20.0	>20.0-25.0	>25.0
	counts/mm ³	10800-15000	>15000-20000	>20000-25000	>25000

^[1] Preferred, defined on actual values. ^[2] Alternative; decrease implies negative changes. Only one should be computed, either ^[1] or ^[2].

 FLU010	Statistical Analysis Plan										
	Final analysis								Final 3.0 of 15JUN2020		

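### The SAP grades bilirubin on one row for everyone and omits the protocol's stricter row for bilirubin raised together with a liver function test

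*SAP*

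**What the plan says.** Protocol 9.1.3 has laboratory changes from baseline evaluated on the appended toxicity scale, with laboratory normal ranges used only for parameters that have no grades. In that scale (Protocol Appendix 2, part B) bilirubin has two rows. One is headed "Bilirubin – when accompanied by any increase in Liver Function Test increase by factor", with a Grade 3 band of "1.51 – 1.75 x ULN" and Grade 4 above that. The other is headed "Bilirubin – when Liver Function Test is normal; increase by factor", with Grade 3 at 2.0–3.0 x ULN and Grade 4 above 3.0.

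SAP 3.2.2 names the same source: "Toxicity grades will be computed according to the Centre for Biologics Evaluation and Research (CBER) toxicity grading list". It then restricts the programming: "Only the parameters described in appendix 9.2 will be computed, according to the declared limits for each grade". Appendix 9.2 is the influenza symptom score card; the grading table is Appendix 9.3. That table has one row for total bilirubin, with no condition on any other test. SAP 6.1, the place for changes not covered by protocol amendments before database lock, contains only the entry NAP.

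The grades feed two outputs: the line for treatment-emergent Grade 3 or higher laboratory toxicity in the safety overview (SAP 3.1.3), and the cross-tabulations against baseline with counts of treatment-emergent toxicities (SAP 3.2.3).

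**The concern.** The protocol grades bilirubin more strictly when it rises together with transaminases than when it rises alone. A programmer who follows the SAP cannot apply that distinction, because only the rows in its appendix may be computed and the conditional row is not there. The data needed are available: bilirubin, ALT and AST belong to the same biochemistry panel (SAP 3.2.1). No planned SAP table considers bilirubin and transaminases jointly, so the conditional row is the only grading in either document that would show the combined pattern. What is at stake is the tabulated grade, and for part of the range the Grade 3 or higher count, of a joint liver signal.

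**Working it through.** **Inputs (upper limits in multiples of ULN; Grade 1 starts at 1.1 in every row)**

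| Row | Grade 1 | Grade 2 | Grade 3 | Grade 4 |
|---|---|---|---|---|
| Protocol Appendix 2, liver test also raised | 1.1–1.25 | 1.26–1.5 | 1.51–1.75 | >1.75 |
| Protocol Appendix 2, liver test normal | 1.1–1.5 | 1.6–2.0 | 2.0–3.0 | >3.0 |
| SAP 9.3, total bilirubin | 1.1–1.5 | >1.5–2.0 | >2.0–3.0 | >3.0 |

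**Step 1: where the SAP row comes from.** The protocol prints bands with small gaps (1.5 to 1.6) and prints 2.0 in two grades. The SAP closes these with continuous cut-points. On that convention the cut-points of the SAP row and of the protocol's normal-liver-test row are the same: 1.5, 2.0 and 3.0. The SAP row is therefore the looser protocol row, applied to everyone.

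**Step 2: compare with the strict row.** The same continuous convention is used for the strict row (cut-points 1.25, 1.5 and 1.75). Shortfall = protocol grade − SAP grade, when ALT or AST is also raised:

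| Bilirubin (x ULN) | SAP grade | Protocol grade | Shortfall |
|---|---|---|---|
| 1.1–1.25 | 1 | 1 | 0 |
| >1.25–1.5 | 1 | 2 | 1 |
| >1.5–1.75 | 2 | 3 | 1 |
| >1.75–2.0 | 2 | 4 | 2 |
| >2.0–3.0 | 3 | 4 | 1 |
| >3.0 | 4 | 4 | 0 |

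A scan from 1.00 to 4.00 x ULN in steps of 0.01 gives the same change points.

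**Step 3: effect on the Grade 3 or higher line.** The strict row reaches Grade 3 above 1.5 x ULN, the SAP row above 2.0. Only >1.5–2.0 x ULN drops out. At >2.0–3.0 the SAP grade is 3 instead of 4 and is still counted.

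**Step 4: an example.** Take ALT 3 x ULN and bilirubin 1.8 x ULN. ALT is Grade 2 in SAP 9.3 (>2.5–5.0). Bilirubin is Grade 2 in the SAP and Grade 4 on the protocol's strict row. With no other Grade 3 abnormality, this participant is absent from the overview line.

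**Step 5: which samples.** In the schedules, Period 1 chemistry is planned only at Screening 2, with unscheduled visits at the Investigator's discretion. Period 2 chemistry is at Day -2 or Day -1, Day 2 and Day 8. Under SAP 5.2.1 the vaccination phase runs until one minute before challenge, so the pre-challenge draw falls in that phase, at least 6 weeks after vaccination. Days 2 and 8 fall in the challenge phase.

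**The case against.** The best case for leaving the SAP alone is that little is hidden. ALT and AST are graded on their own rows in SAP 9.3. All laboratory data are listed for any subject with a post-baseline abnormality (SAP 3.2.3). The investigator reviews every result and records clinically relevant changes as adverse events (Protocol 7.2.3). Appendix 2 describes its laboratory limits as guidelines. No endpoint or hypothesis test uses these grades. All of this stands and limits the consequence. It does not explain why one protocol row is carried over and the other is dropped without a declaration.

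A reader might infer more than the documents support:

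- *That these cases vanish from the shift tables.* They do not. SAP 3.2.3 cross-tabulates every grade, so they appear there at a lower grade.
- *That vaccine and challenge assessments are equally affected.* The only scheduled chemistry between vaccination and challenge is the pre-challenge draw.
- *That halting decisions are affected.* Protocol 8.3 ties the challenge rule on Grade 3 or 4 laboratory abnormalities to relatedness and to concern of the Investigator or Medical Monitor. Nothing links it to SAP-derived grades.
- *That haemoglobin has the same fault.* The protocol also has a row "Hemoglobin (Female) change from baseline value - gm/dL" (and one for men), and the SAP prefers actual values. But SAP 9.3 shows both versions and says "Only one should be computed, either" one or the other. That is an open choice between two rows of the same scale, and changes from baseline are still summarised.
- *That a raised alkaline phosphatase should trigger the strict row.* Appendix 2 labels liver function tests as ALT and AST and gives alkaline phosphatase a separate row.

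**Conclusion.** The point holds for bilirubin. SAP 9.3 departs from the scale that Protocol 9.1.3 requires, without saying so. With ALT or AST raised, the SAP bilirubin grade is one or two grades too low from just above 1.25 up to 3.0 x ULN, and correct outside that range. Bilirubin of >1.5–2.0 x ULN in such participants is missed as Grade 3 or higher, and the participant is lost from the overview count unless another parameter reaches Grade 3.

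This rests on two assumptions: that liver function test means ALT and AST, as Appendix 2 labels them, and that the printed bands are read as continuous in the way the SAP reads them. The number of participants affected cannot be estimated, because the documents give no bilirubin or transaminase rates. The consequence is confined to descriptive safety tables, but those tables would not follow the protocol's scale for this pattern.

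**What to change.** In SAP 9.3, replace the single bilirubin row with the two Appendix 2 rows, the strict one applying when ALT or AST is raised at the same time. State what counts as raised, because the protocol does not define it: for example above ULN, or from 1.1 x ULN where the ALT/AST grades begin. State also whether the values must come from the same sample. If the single row is intended, record it in SAP 6.1 as a departure from Protocol 9.1.3 and give the reason. In either case, change the references in SAP 3.2.2 from appendix 9.2 to 9.3.

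The cost is a conditional statement in the laboratory grading program, one extra table row and a corrected reference. No new data are needed.

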3.2.3 Presentation of results

The statistical analysis will present results in standardised units.

Continuous laboratory parameters will be summarised by means of descriptive statistics at each analysis visit. Actual values and changes from baseline will be tabulated separately. Categorical parameters will be listed only.

Laboratory toxicity grades will be presented as cross-tabulations of the toxicity at each post-baseline analysis visit and at the worst-case analysis visit versus the baseline toxicity. Numbers and cumulative numbers of subjects with treatment-emergent toxicities will also be shown. Parameters having toxicity grades defined in both directions (hypo and hyper) will be shown by direction.

For laboratory parameters, laboratory abnormalities will be presented as cross-tabulations of the abnormality at each post-baseline analysis visit and at the worst-case analysis visit versus the baseline abnormality. Numbers of subjects with treatment-emergent abnormalities will also be shown.

All laboratory data will be listed, but only for subjects with any post-baseline abnormality or clinical significant value.

Box plots over time of the actual values and of the changes will be prepared for the following parameters: WBC counts and % lymphocytes counts.

3.3 VITAL SIGNS

3.3.1 Available data

The following vital signs parameters are collected: pulse rate, systolic (SBP) and diastolic blood pressure (DBP) in supine position, body temperature, oxygen saturation.

3.3.2 Derivation rules

Abnormalities are defined in below table.

Vital sign	Pulse rate (bpm)		SBP (mmHg)		DBP (mmHg)	Temp (°C)
Abnormality	Tachy cardia	Brady cardia	Hyper tension	Hypo tension	Hyper tension	Fever
Normal	55-100	55-100	90-140	90-140	≤ 90	
Grade 1	101-115	50-54	141-150	85-89	91-95	38.0-38.4
Grade 2	116-130	45-49	151-155	80-84	96-100	38.5-38.9
Grade 3	> 130	< 45	> 155	< 80	> 100	39.0-40.0
Grade 4						> 40.0

	Statistical Analysis Plan	
FLU010	Final analysis	Final 3.0 of 15JUN2020

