9.1.3 Safety Data

Safety parameters will be tabulated and analysed descriptively.

Adverse Events

The original terms used in the eSource documents by Investigators to identify AEs will be fully described and coded according to the Medical Dictionary for Regulatory Activities (MedDRA).

The reported AEs will be allocated to phases based on their start date. All AEs will be listed. All AEs with onset after Day 1 of vaccination will be summarized by treatment group. Summaries, listings, and narratives may be provided, as appropriate. Summaries will include at a minimum SAEs, and for both solicited and unsolicited AEs, the severe (grade 3+ events), related AEs, and AEs following challenge.

Clinical Laboratory Tests

Each continuous biochemistry and haematology laboratory test will be evaluated by means of descriptive statistics (i.e., number of participants, mean, SD, median, minimum, and maximum) on the actual values, at each assessment time point and by vaccination group.

Relative changes in clinical laboratory test values compared to values at baseline will be evaluated according to the appended toxicity scale or in accordance with the normal ranges of the clinical laboratory (below, within, or above normal range) for parameters for which no toxicity grades are defined.

A listing of participants with any clinical laboratory test result outside the reference ranges will be provided.

Vital Signs

Pulse rate, temperature, SBP, and DBP will be evaluated by means of descriptive statistics (actual values and changes from Day 1 to Day 2 of the vaccine phase and from Day 1 of the challenge phase and frequency tabulations at each assessment time point and by vaccination group).

Pulse oximetry will be measured during the entire challenge phase.

The percentage of participants with values beyond clinically important limits (as defined in the Toxicity Tables) will be summarized.

Electrocardiogram

ECG variables will be evaluated by means of descriptive analysis by the Investigator at each assessment time point.

The percentage of participants with ECG abnormalities will be summarized.

The ECG variables that will be analysed by electronic capture from the ECG include heart rate, PR interval, QRS interval, QT interval.

Physical Examination

Abnormal findings in physical examination will be listed.

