APPENDIX 1: ADVERSE EVENTS OF SPECIAL INTEREST

Adverse events of special interest represent a subset of adverse events that include autoimmune diseases and other systemic disorders of interest which could potentially have an autoimmune aetiology. Adverse events of special interest are listed below. The Investigator should use clinical and scientific judgment in deciding whether other adverse events (i.e., events not listed here) could have an autoimmune origin and should therefore be reported as adverse events of special interest.

Bell's Palsy
 Guillain Barre Syndrome
 Myocarditis
 Stevens-Johnson Syndrome

APPENDIX 2: TOXICITY GRADING SCALE FOR HEALTHY ADULT AND ADOLESCENT VOLUNTEERS ENROLLED IN PREVENTIVE VACCINE CLINICAL TRIALS

<https://www.fda.gov/downloads/BiologicsBloodVaccines/ucm091977>

A. TABLES FOR CLINICAL ABNORMALITIES

Local Reaction to Injectable Product	Mild (Grade 1)	Moderate (Grade 2)	Severe (Grade 3)	Potentially Life Threatening (Grade 4)
Pain	Does not interfere with activity	Repeated use of non-narcotic pain reliever > 24 hours or interferes with activity	Any use of narcotic pain reliever or prevents daily activity	Emergency room (ER) visit or hospitalization
Tenderness	Mild discomfort to touch	Discomfort with movement	Significant discomfort at rest	ER visit or hospitalization
Erythema/Redness *	2.5 – 5 cm	5.1 – 10 cm	> 10 cm	Necrosis or exfoliative dermatitis
Induration/Swelling **	2.5 – 5 cm and does not interfere with activity	5.1 – 10 cm or interferes with activity	> 10 cm or prevents daily activity	Necrosis

* In addition to grading the measured local reaction at the greatest single diameter, the measurement should be recorded as a continuous variable.

** Induration/Swelling should be evaluated and graded using the functional scale as well as the actual measurement.

Vital Signs *	Mild (Grade 1)	Moderate (Grade 2)	Severe (Grade 3)	Potentially Life Threatening (Grade 4)
Fever (°C) ** (°F) **	38.0 – 38.4 100.4 – 101.1	38.5 – 38.9 101.2 – 102.0	39.0 – 40 102.1 – 104	> 40 > 104
Tachycardia - beats per minute	101 – 115	116 – 130	> 130	ER visit or hospitalization for arrhythmia
Bradycardia - beats per minute***	50 – 54	45 – 49	< 45	ER visit or hospitalization for arrhythmia
Hypertension (systolic) - mm Hg	141 – 150	151 – 155	> 155	ER visit or hospitalization for malignant hypertension
Hypertension (diastolic) - mm Hg	91 – 95	96 – 100	> 100	ER visit or hospitalization for malignant hypertension

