Hypotension (systolic) – mm Hg	85 – 89	80 – 84	< 80	ER visit or hospitalization for hypotensive shock
Respiratory Rate – breaths per minute	17 – 20	21 – 25	> 25	Intubation

* Participant should be at rest for all vital sign measurements.

** Oral temperature; no recent hot or cold beverages or smoking.

*** When resting heart rate is between 60 – 100 beats per minute. Use clinical judgement when characterizing bradycardia among some healthy participant populations, for example, conditioned athletes.

Systemic (General)	Mild (Grade 1)	Moderate (Grade 2)	Severe (Grade 3)	Potentially Life Threatening (Grade 4)
Nausea/vomiting	No interference with activity or 1 – 2 episodes/24 hours	Some interference with activity or > 2 episodes/24 hours	Prevents daily activity, requires outpatient IV hydration	ER visit or hospitalization for hypotensive shock
Diarrhea	2 – 3 loose stools or < 400 gms/24 hours	4 – 5 stools or 400 – 800 gms/24 hours	6 or more watery stools or > 800gms/24 hours or requires outpatient IV hydration	ER visit or hospitalization
Headache	No interference with activity	Repeated use of non-narcotic pain reliever > 24 hours or some interference with activity	Significant; any use of narcotic pain reliever or prevents daily activity	ER visit or hospitalization
Fatigue	No interference with activity	Some interference with activity	Significant; prevents daily activity	ER visit or hospitalization
Myalgia	No interference with activity	Some interference with activity	Significant; prevents daily activity	ER visit or hospitalization

Systemic Illness	Mild (Grade 1)	(Moderate (Grade 2)	Severe (Grade 3)	Potentially Life Threatening (Grade 4)
Illness or clinical adverse event (as defined according to applicable regulations)	No interference with activity	Some interference with activity not requiring medical intervention	Prevents daily activity and requires medical intervention	ER visit or hospitalization

B. TABLES FOR LABORATORY ABNORMALITIES

The laboratory values provided in the tables below serve as guidelines and are dependent upon institutional normal parameters. Institutional normal reference ranges should be provided to demonstrate that they are appropriate.

Serum *	Mild (Grade 1)	Moderate (Grade 2)	Severe (Grade 3)	Potentially Life Threatening (Grade 4)**
Sodium – Hyponatremia mEq/L	132 – 134	130 – 131	125 – 129	< 125
Sodium – Hypernatremia mEq/L	144 – 145	146 – 147	148 – 150	> 150
Potassium – Hyperkalemia mEq/L	5.1 – 5.2	5.3 – 5.4	5.5 – 5.6	> 5.6

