RBC	red blood cells

	Statistical Analysis Plan	
FLU010	Final analysis	Final 3.0 of 15JUN2020

RND	all randomised subjects analysis set
SAE	serious adverse event
SAP	statistical analysis plan
SAF	safety analysis set
SCR	all screened subjects analysis set
SFC	spot-forming colony
SGS LS	SGS Life Sciences
SOP	standard operating procedure
SSC	symptom score card
STAT	statistics
TEAE	treatment-emergent adverse event
TOEP(H)	(heterogeneous) Toeplitz
UN	unstructured
vAUC	viral area under the curve (as determined by qPCR)
WBC	white blood cells
WI	work instruction

	Statistical Analysis Plan	
FLU010	Final analysis	Final 3.0 of 15JUN2020

DEFINITION OF TERMS

case report form (CRF)	A printed, optical, or electronic document designed to record protocol required information to be reported to the sponsor for each trial subject.
display	Analysis table, figure or listing
phase	Interval of time in the planned conduct of a study associated with a specific purpose: for example, screening, treatment, follow-up.
study drug	Pharmaceutical form of an active ingredient or placebo, being tested or used as a reference in a clinical study.
treatment-emergent abnormality	Any post-baseline abnormality that was not present at baseline (e.g. haemoglobin normal at baseline and grade 1 post-baseline; glucose grade 1 at baseline and grade 3 post-baseline). Abnormalities in vaccination phase are evaluated versus vaccination baseline. Post-challenge abnormalities are evaluated versus challenge baseline.
Within 2 consecutive days	Whenever in the endpoint definition it is mentioned that two positive samples/symptoms have to occur 'within 2 consecutive days', this includes the following cases:

Day x am	Day x pm	Day x+1 am	Day x+1 pm	
pos	pos	neg	neg	Two consecutive + on the same day
neg	pos	pos	neg	Two consecutive + on consecutive days
pos	neg	neg	pos	Two + on two consecutive days with intermittent - sample(s)

	Statistical Analysis Plan	
FLU010	Final analysis	Final 3.0 of 15JUN2020

TABLE OF CONTENTS

Signature page	2
Protocol history	3
List of abbreviations	4
Definition of terms	6
Table of contents	7
1. Introduction	11
1.1 Study objectives.....	11
1.2 Study design	12
1.3 Expected sample size.....	12
1.4 Randomisation and blinding.....	13
1.5 Interim analysis	13
1.6 Software.....	13
1.7 Validation model	14
2. Efficacy and immunogenicity analyses	15
2.1 Efficacy.....	15
2.1.1 Available data.....	15
2.1.2 Endpoints and derivation rules.....	16
2.1.2.1 Primary endpoint.....	16

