3.3.3 Presentation of results

All tables will be presented by analysis phase (vaccination / challenge). Analysis phases are defined in section 5.2.1.

Vital signs parameters will be summarised by means of descriptive statistics at each analysis visit. Actual values and changes from baseline will be tabulated separately.

Abnormalities will be presented as cross-tabulations of the abnormality at each post-baseline analysis visit versus the baseline abnormality and as cross-tabulations of the worst-case abnormality versus the baseline abnormality. Numbers of subjects with treatment-emergent abnormalities will also be shown.

All vital signs data will be listed, but only for subjects with any post-baseline abnormality or clinical significant value.

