3.4.2 Derivation rules

Abnormalities for HR, QRS and PR interval are defined in below table.

	HR (bpm)	PR (ms)	QRS (ms)
Low	< 40	< 110	-
Normal	40-100	110-220	≤ 120
High	> 100	> 220	> 120

Note: For the worst-case analysis visit, as defined in section 5.2.5, an additional category low + high is defined in case there are both low and high values within the same phase.

For QTc interval (ms), the following categories are defined:

- Actual values:
 - ≤ 450 (normal)
 -]450; 480]
 -]480; 500]
 - > 500
- Changes:
 - ≤ 30 (normal)
 -]30; 60]
 - > 60

Note: The worst-case, as defined in section 5.2.5, is the highest value and associated change.

	Statistical Analysis Plan	
FLU010	Final analysis	Final 3.0 of 15JUN2020

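### SAP 3.3.2 grades bradycardia in every participant and omits the 60–100 bpm resting-rate condition of Protocol Appendix 2, which inflates counts in one descriptive safety table

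*SAP*

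**What the plan says.** Protocol 9.1.3 (Vital Signs) fixes the source of the limits: "The percentage of participants with values beyond clinically important limits (as defined in the Toxicity Tables) will be summarized".

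Those tables are in Protocol Appendix 2, part A. The row "Bradycardia - beats per minute" carries a three-star marker and gives 50–54 (Grade 1), 45–49 (Grade 2) and below 45 (Grade 3). The three-star footnote limits its use: "When resting heart rate is between 60 – 100 beats per minute". It continues: "Use clinical judgement when characterizing bradycardia among some healthy participant populations, for example, conditioned athletes".

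SAP 3.3.2 introduces its own table with "Abnormalities are defined in below table". The bradycardia cut-offs are the same, 55–100 is called normal, and there is no footnote and no baseline condition. The SAP's toxicity appendix (9.3) covers laboratory parameters only, so it does not bring the condition back. SAP 6.1 and 6.2 both record no changes to the planned analysis.

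SAP 3.3.3 presents "cross-tabulations of the worst-case abnormality versus the baseline abnormality", with numbers of treatment-emergent abnormalities. The SAP's Definition of terms gives treatment-emergent as "Any post-baseline abnormality that was not present at baseline", and its glucose example shows that a worse grade than at baseline also counts. SAP 5.2.5 takes the worst case within each phase and includes unscheduled readings.

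**The concern.** The protocol's scale is conditional and the SAP's is not, yet the SAP presents itself as following the protocol. The study population is healthy adults aged 18–55, measured supine after five minutes' rest (Protocol 7.2.4), so resting rates below 60 are to be expected. Some of these people will be counted with treatment-emergent bradycardia, occasionally Grade 3, although the protocol's scale would give them no grade. What is at stake is how the absolute counts in Table 14.3.3.3 are read. A reader who takes them as Appendix 2 grades will see more bradycardia than that scale would report.

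**Working it through.** The plan states no bradycardia count, so there is no figure to reproduce. The check has two parts: the rules applied to single participants, then an illustrative simulation.

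**1. Meaning of the condition.** A reading of 50–54 cannot itself lie in 60–100, so the footnote must refer to the participant's usual or baseline rate. Phase baseline (SAP 5.2.2) is used for this below. That is an interpretation, since Appendix 2 does not define the term.

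**2. Single participants (bpm).**

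| Baseline | Worst later | SAP 3.3.2 | Treatment-emergent in SAP | Appendix 2 with condition |
|---|---|---|---|---|
| 57 | 53 | normal to Grade 1 | yes | not graded |
| 52 | 44 | Grade 1 to Grade 3 | yes, Grade 3 | not graded |
| 52 | 51 | Grade 1 to Grade 1 | no | not graded |
| 60 | 54 | normal to Grade 1 | yes | Grade 1, also counted |

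The first two rows are the discrepancy. The third shows that a stable slow pulse is already left out. The fourth shows that the condition does not remove ordinary variation in everyone.

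**3. Number of readings.** The Period 2 schedule has vital signs on Days 2 to 11 (10 readings) and Day 28 (1), so 10 + 1 = 11 after inoculation, or 12 if the Day 1 reading is taken afterwards. The Period 1 schedule has two post-vaccination visits (Days 8 and 28). Pre-inoculation readings also fall in the vaccination phase under SAP 5.2.1, so two is a minimum.

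**4. Simulation.** All pulse inputs are assumptions: mean 62, 66 or 70; between-person SD 8 or 10; within-person SD 4 or 6; normal; rounded to integers; no effect of vaccine or challenge. This gives 3 × 2 × 2 = 12 scenarios, with 400,000 simulated people each. N = 155 vaccinated and 134 challenged come from the protocol.

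- Treatment-emergent: worst grade over the readings is higher than the baseline grade.
- SAP count = N × P(treatment-emergent).
- Conditional count = N × P(treatment-emergent and baseline 60–100).
- Share from baseline below 60 = 1 − conditional count / SAP count.

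Ranges over the 12 scenarios, in participants, both arms together:

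| Readings, N | Grade | SAP rule | Baseline 60–100 only |
|---|---|---|---|
| 2, 155 | any | 6.9–35.0 | 2.5–14.2 |
| 2, 155 | 3 | 0.4–9.5 | 0.01–0.96 |
| 12, 134 | any | 16.3–68.6 | 7.4–32.6 |
| 12, 134 | 3 | 1.3–22.9 | 0.05–3.76 |

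With 11 readings instead of 12 the counts cannot be higher.

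One middle scenario (mean 66, SDs 8 and 4, 12 readings):

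- Any grade: 31.0 against 12.0, a share of (31.0 − 12.0) / 31.0 = 61%.
- Grade 3: 3.9 against 0.12, a share of (3.9 − 0.12) / 3.9 = 97%.

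Over all scenarios and both reading counts, 12–41% of participants have a baseline below 60. They supply 37–80% of any-grade treatment-emergent bradycardia and about 74–99% of Grade 3.

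**The case against.** The strongest reply is that the SAP already limits the effect. The baseline comparison removes a stable slow pulse: among simulated participants with baseline below 55, 73–83% are not treatment-emergent with two readings and 44–55% with twelve. This stands, but it leaves a baseline of 55–59 falling below 55, and a slow pulse falling a further grade.

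Four stronger readings are tempting, and the documents do not support them.

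- *Slow-pulse participants make up most of the counts.* There are no pulse data, and at any grade their share runs from 37% to 80% by assumption. Only the Grade 3 share is consistently high, and it rests on the same assumptions.
- *The comparison between arms is biased.* With randomisation the excess is expected in proportion in both arms, and safety is analysed descriptively. The excess adds noise and raises absolute counts.
- *A myocarditis signal would be hidden, or Grade 3 adverse events inflated.* Protocol 7.2.6 looks for myocarditis on ECG. Section 7 calls for ECG and troponin for a suspected cardiac event, Appendix 1 lists myocarditis as an event of special interest, and 8.3 halts challenge on suspicion. The adverse-event overview in SAP 3.1.3 does not count vital-sign grades. Under Protocol 7.2.4 a pulse change becomes an adverse event only if the investigator judges it clinically relevant.
- *The SAP's ECG table contradicts its pulse table.* SAP 3.4.2 says "Abnormalities for HR, QRS and PR interval are defined in below table" and calls 40–100 bpm normal, so 44 bpm is normal there and Grade 3 as a pulse. But ECG heart rate is a separate measurement classed as low, normal or high, and the protocol sets no limit for it. The difference would remain after the pulse table is corrected.

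Leaving participants with baseline below 60 ungraded would also have a cost: a fall from 58 to 40 would drop out of the graded counts.

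**Conclusion.** The mismatch needs no assumption. SAP 3.3.2 applies the Appendix 2 cut-offs without the Appendix 2 condition, and section 6 does not declare it. Table 14.3.3.3 will therefore include treatment-emergent bradycardia that the protocol's scale would not grade. The direction is inflation of absolute counts in both arms, clearest at Grade 3 and in the challenge phase, where the worst of about 11 scheduled readings is taken. The size is uncertain. The simulated ranges depend on the assumed pulse distribution, on no change in pulse after a challenge with an expected attack rate of about 83%, and on reading resting rate as phase baseline. The effect is confined to one descriptive cross-tabulation and its listing. This is a consistency correction and does not threaten the trial's safety conclusions.

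**What to change.** In SAP 3.3.2 and Table 14.3.3.3, show worst-case and treatment-emergent bradycardia counts separately for phase-baseline pulse 60–100 bpm (the protocol's scale) and below 60. Add a footnote stating the Appendix 2 condition and that phase baseline stands for the resting rate. Note any baseline above 100 or missing so that the rows add up. The clinical-judgement part of the footnote cannot be programmed, and the new footnote should say so.

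Keep every low value in the listing. SAP 3.3.3 lists only participants with an abnormality or a clinically significant value, so an ungraded participant could otherwise disappear from it. If everyone is still graded together, declare and justify the departure in SAP section 6.

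The cost is one extra split in one table, with no new data. Cells in the below-60 group will be small. Challenge baseline is measured after randomisation, so the split should be read descriptively.
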